Initiating tofacitinib with ≥1 VTE risk factor(s)	Outcome: changes in use in patients with VTE risk factors	Defined as ≥1 VTE risk factor(s) (as listed and defined above) identified in the 12 months prior to the index tofacitinib dispensing.
Initiating tofacitinib with ≥1 VTE risk factors other than CV or malignancy risk factors	Outcome: changes in use in patients with VTE risk factors	The same definition as above but only limited to VTE risk factors other than CV or malignancy risk factors.
VTE risk factor scores	Outcome: changes in use in patients with VTE risk factors	Calculated as the sum of the number of VTE risk factors (as listed and defined above) identified in the 12 months prior to the index tofacitinib dispensing. Weighting of VTE risk factors may be considered as a sensitivity analysis to reflect the potential different
Number of UC patients with: ≥1 VTE risk factor; no prior alternative therapy (i.e., biologic); and an ADD >10 mg in Weeks 17-24, Weeks 25-32, Weeks 33-40 or Weeks 41-48 of follow-up	Outcome: changes in use in patients with VTE risk factors	importance of each risk factor. Defined as an UC patient meeting all of the following criteria: ≥1 VTE risk factor(s) (as listed and defined above) 12 months prior to the index tofacitinib prescription dispensing; 0 prescription medication dispensing for a biologic (as identified by ATC codes) in the 12 months prior to the index tofacitinib prescription dispensing; and an ADD of >10 mg in any of the intervals: Weeks 17-24, Weeks 25-32, Weeks 33-40 and Weeks 41-48 of follow-up (ADD defined in Section 9.3.3). Complete list of biologics in ANNEX 7. LIST OF ATC CODES FOR MEDICATIONS OF INTEREST TO AVOID WHILE TAKING TOFACITINIB.
Assessment of VTE risk; Section 9.3.2)	factors while receiving	tofacitinib therapy (duration of tofacitinib therapy defined in
VTE	Outcome: changes in use in patients with VTE risk factors	Defined as ≥1 ICD-10 diagnosis code for VTE while receiving tofacitinib therapy. List of VTE codes in ANNEX 12. LIST OF DIAGNOSIS CODES FOR VTE

Table 3. Operational definitions of study variables in Système National des Données de Santé

Variable	Role	Operational definition
Surgery, major	Outcome: changes in use in patients with VTE risk factors	Defined as ≥1 procedure code for a major surgery while receiving tofacitinib therapy.
MI	Outcome: changes in use in patients with VTE risk factors	Defined as ≥1 ICD-10 diagnosis code for an MI while receiving tofacitinib therapy.

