Heart failure	Outcome: changes in use in patients with VTE risk factors	Defined as ≥1 ICD-10 diagnosis code for heart failure while receiving tofacitinib therapy.
Use of combined hormonal contraceptives or hormonal replacement therapy	Outcome: changes in use in patients with VTE risk factors	Defined as ≥1 prescription dispensing of a combined hormonal contraceptives and/or hormonal replacement therapy (as identified by ATC codes) while receiving tofacitinib therapy.
Inherited coagulation disorder	Outcome: changes in use in patients with VTE risk factors	Defined as ≥1 ICD-10 diagnosis code for inherited coagulation disorder while receiving tofacitinib therapy.
Malignancy (non- metastatic and metastatic, excluding NMSC)	Outcome: changes in use in patients with VTE risk factors	Defined as ≥1 ICD-10 diagnosis code for malignancy (excluding NMSC) while receiving tofacitinib therapy.
Age ≥ 65 years	Outcome: changes in use in patients with VTE risk factors	Defined as age ≥65 years while receiving to facitinib.
Diabetes	Outcome: changes in use in patients with VTE risk factors	Defined as ≥1 ICD-10 diagnosis code for diabetes or ≥3 (or at least 2 in case of large pack sizes) prescription dispensing of oral antidiabetic agents and/or insulin (identified by ATC codes) while receiving tofacitinib therapy.
Hypertension	Outcome: changes in use in patients with VTE risk factors	Defined as ≥1 ICD-10 diagnosis code for hypertension or ≥3 (or at least 2 in case of large pack sizes) prescription dispensing of antihypertensive agents (identified by ATC codes) while receiving tofacitinib therapy.
Discontinuation of tofacitinib after developing ≥1 VTE risk factors while taking tofacitinib	Outcome: changes in use in patients with VTE risk factors	Defined as ≥1 VTE risk factor(s) while receiving tofacitinib therapy (as listed and defined above) plus 0 prescription dispensing for tofacitinib within a specific time window after the code for the first VTE risk factor.
g		Note: The time window for when to look for a tofacitinib prescription dispensing will be specific to the VTE risk factor(s) acquired while receiving tofacitinib therapy and will be operationalised during SAP development.
		Duration of tofacitinib therapy defined in Section 9.3.2.

Table 3. Operational definitions of study variables in Système National des Données de Santé

Variable Role Operational definition	
Discontinuation of Outcome: changes The same definition as above but of	only limited to VTE risk

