Variable	Role	Operational definition
Continuation of	Outcome: changes	Defined as patients aged <65 years when initiating
tofacitinib for patients	in use in patients	tofacitinib, who have ≥1 prescription dispensing of
who turn 65 years old	aged 65 years and	tofacitinib within a specific time window after turning 65
while receiving	older	years and ≥1 prescription dispensing for an alternative
tofacitinib with prior		therapy (i.e., biologic) prior to index tofacitinib prescription
use of alternative		dispensing.
therapies		
	endations for limitation	ons of use in patients with CV risk factors (will be stratified
		, and CV and malignancy report period 1, 2, 3)
Assessment of CV risk for	actors prior to initiation	n of tofacitinib
History of	Outcome: changes	Defined as ≥1 ICD-10 diagnosis code for hyperlipidaemia or
hyperlipidaemia	in use in patients	≥1 prescription dispensing (as identified by ATC code[s]) for
	with CV risk	a statin or other antihyperlipidaemic in the 12 months prior
	factors	to the index tofacitinib dispensing.
		Complete list in ANNEX 9. LIST OF ATC CODES FOR
		ANTIHYPERLIPIDAEMICS.
Age ≥65 years	Outcome: changes	Defined as age at tofacitinib initiation ≥65 years
	in use in patients	
	with CV risk	
	factors	
History of coronary	Outcome: changes	Defined as ≥1 ICD-10 diagnosis code for MI or stroke or ≥1
artery disease (defined	in use in patients	procedure code for CABG or PCI in the 12 months prior to
as MI, stroke,	with CV risk	the index tofacitinib dispensing.
coronary artery bypass	factors	
graft [CABG] or		
percutaneous coronary		
intervention [PCI])		
History of stable	Outcome: changes	Defined as ≥1 ICD-10 code for stable angina pectoris in the
angina pectoris	in use in patients	12 months prior to the index tofacitinib dispensing.
	with CV risk	
	factors	
Current or past	Outcome: changes	Defined as ≥1 ICD-10 diagnosis code for tobacco use
smoker ¹	in use in patients	disorder or ≥1 procedure code for counselling visits for
	with CV risk	smoking or ≥1 prescription dispensing (as identified by ATC
	factors	code[s]) for a nicotine replacement product in the 12 months
		prior to the index tofacitinib dispensing.
History of diabetes	Outcome: changes	Defined as ≥1 ICD-10 diagnosis code for diabetes or at least
	in use in patients	3 reimbursements (or at least 2 in case of large pack sizes) of
	with CV risk	oral antidiabetic agents and/or insulin in the 12 months prior
	factors	to the index tofacitinib dispensing.

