Hyperlipidaemia	Outcome: changes in use in patients with CV risk factors	Defined as ≥1 ICD-10 diagnosis code for hyperlipidaemia or ≥1 prescription dispensing (as identified by ATC code[s]) for a statin or other antihyperlipidaemic while receiving tofacitinib. Complete list in ANNEX 9. LIST OF ATC CODES FOR ANTIHYPERLIPIDAEMICS.
Age ≥65 years	Outcome: changes in use in patients with CV risk factors	Defined as age ≥65 years while receiving tofacitinib.
Current smoker	Outcome: changes in use in patients with CV risk factors	Defined as ≥1 ICD-10 diagnosis code for tobacco use disorder or ≥1 procedure code for counselling visits for smoking or ≥1 prescription dispensing (as identified by ATC code[s]) for a nicotine replacement product while receiving tofacitinib.
Coronary artery disease (defined as MI, stroke, CABG or PCI)	Outcome: changes in use in patients with CV risk factors	Defined as ≥1 ICD-10 diagnosis code for MI or stroke or ≥1 procedure code for CABG or PCI while receiving tofacitinib therapy.

Table 3. Operational definitions of study variables in Système National des Données de Santé

Variable	Role	Operational definition
Stable angina pectoris	Outcome: changes	Defined as ≥1 ICD-10 diagnosis code for stable angina
8 ₁	in use in patients	pectoris while receiving tofacitinib therapy.
	with CV risk	
	factors	
Diabetes	Outcome: changes	Defined as ≥1 ICD-10 diagnosis code for diabetes while
	in use in patients	receiving tofacitinib therapy.
	with CV risk	
	factors	
Hypertension	Outcome: changes	Defined as ≥1 ICD-10 diagnosis code for hypertension or ≥1
	in use in patients	prescription dispensing (as identified by ATC code[s]) for an
	with CV risk	antihypertensive while receiving tofacitinib.
	factors	Complete list in ANNEX 8. LIST OF ATC CODES FOR
		ANTIHYPERTENSIVES.
Chronic kidney	Outcome: changes	Defined as ≥1 ICD-10 diagnosis code for chronic kidney
disease	in use in patients	disease while receiving tofacitinib.
	with CV risk	
Discontinuation of	factors	Defined as >1 CV misk featon(a) while massiving tofesitinih
tofacitinib after	Outcome: changes	Defined as ≥1 CV risk factor(s) while receiving to facitinib therapy (as listed and defined above) plus 0 prescription
	in use in patients with CV risk	dispensing for tofacitinib within a specific time window after
developing ≥1 CV risk factors while taking	factors	the code for the first CV risk factor.
tofacitinib	Tactors	the code for the first C v fisk factor.

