ANNEX 11. LIST OF CODES FOR COMORBIDITIES

Comorbidity	Definition	Codes (ICD-10 codes, ATC codes, CCAM procedure codes)
Hepatic impairment	Defined as ≥1 ICD-10 diagnosis code for hepatic impairment.	K71 and K72
Renal impairment	Defined as ≥1 ICD-10 diagnosis code for renal impairment or a combination of EBM service	Stage III, IV or V (end stage) Chronic kidney disease
	codes, ICD-10 diagnosis codes and/or ICD-10 procedure codes.	ICD-10 diagnosis: Specific diagnoses of CKD Stage 3: N183 Stage 4: N184 Stage 5: N185 Other chronic renal disease: N188 and N189
		Diagnoses linked to CKD stage 5 Hypertensive cardionephropathy, with renal failure: I131 and I132 Extra-corporeal dialysis: Z491 Preparatory care for dialysis: Z490 Failure and rejection of a kidney transplant: T861 Dependence to kidney dialysis: Z992+1
		CCAM codes for medical procedures due to kidney failure (stage 5): JVJF002, JVJF004, JVJF003, JVJF005, JVJF006, JVJF007, JVJF008, JVRP004, JVRP007, JVRP008 and YYYY007 [TBC IN LAST VERSION]
Diabetes	Defined as ≥1 ICD-10 diagnosis code for diabetes or at least 3 reimbursements (or at least 2 in case of large pack sizes) of oral antidiabetes agents and/or insulin.	ICD-10 diagnosis: E10-E14 ATC code medications: A10*
Herpes zoster	Defined as ≥1 ICD-10 diagnosis code for herpes zoster.	B02*
Human immunodeficiency virus	Defined as ≥1 ICD-10 diagnosis code for human immunodeficiency virus.	B20-B24 and Z21
Tuberculosis, including both active and latent TB	Defined as ≥1 ICD-10 diagnosis code for tuberculosis.	
Viral hepatitis B or C	Defined as ≥1 ICD-10 diagnosis code for viral hepatitis B or C.	B180, B181 and B182

Comorbidity	Definition	Codes (ICD-10 codes, ATC codes, CCAM procedure codes)
Diverticulitis	Defined as ≥1 ICD-10 diagnosis code for diverticulitis.	Q396, Q696, K225, K382, N323, Q430, K314, N361 and C173
Malignancy (non-metastatic and metastatic, excluding non-melanoma skin cancer)	Defined as ≥1 ICD-10 diagnosis code for a malignancy (excluding non-melanoma skin cancer).	See table below
Non-melanoma skin cancer	Defined as ≥1 ICD-10 diagnosis code for non-melanoma skin cancer.	C44 other malignant tumour of the skin
Gastrointestinal perforation	Defined as ≥1 ICD-10 diagnosis code for gastrointestinal perforation.	K285

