Hypertension	Defined as ≥1 ICD-10 diagnosis code for hypertension or at least 3 reimbursements (or at least 2 in case of large pack sizes) of antihypertensive in the 12 months prior to or on the day of the index tofacitinib dispensing.	I10-I15
Prior myocardial infarction	Defined as ≥1 ICD-10 diagnosis code for a myocardial infarction in the 3 months prior to or on the day of the index tofacitinib dispensing.	I20-I25
Heart failure	Defined as ≥1 ICD-10 diagnosis code for heart failure in the 12 months prior to or on the day of the index tofacitinib dispensing.	I50, I110, I130 and I132
Inherited coagulation disorder	Defined as ≥1 ICD-10 diagnosis code for inherited coagulation disorder while receiving tofacitinib therapy.	D680, D681, D682, D66, D67, D689 and D686
Coronary heart disease	Defined as ≥1 ICD-10 diagnosis code for coronary heart disease.	I20-I25, I77 and Z95
Stable angina pectoris	Defined as ≥1 ICD-10 diagnosis code for stable angina pectoris.	I208 and I209
Hypercholesterolemia or dyslipidaemia or atherosclerosis	Defined as ≥1 ICD-10 diagnosis code for hypercholesterolemia or dyslipidaemia or atherosclerosis and ATC codes LLTs (statins, fibrates etc).	ICD-10: E780, E782, E783, E784, E785, E788, E789, Z863 and I70 ATC codes Statins: C10BA05, C10AA04 C10AA02, C10AA08, C10AA03, C10AA07 and C10AA01 ATC codes Fibrates: C10AB
Epstein-Barr virus (EBV)	Defined as ≥1 ICD-10 diagnosis code for Epstein-Barr virus.	D823, B348, B270, P358 and Z228
Hepatitis B virus (HBV)	Defined as ≥1 ICD-10 diagnosis code for Hepatitis B virus.	B181
Human papillomavirus (HPV)	Defined as ≥1 ICD-10 diagnosis code for HPV.	A630

Comorbidity	Definition	Codes (ICD-10 codes, ATC codes, CCAM procedure codes)
Human T-cell lymphotropic virus (HTLV)	Defined as ≥1 ICD-10 diagnosis code for human T-cell lymphotropic virus.	Z226, L303, B333 and B973
Hepatitis C virus (HCV)	Defined as ≥1 ICD-10 diagnosis code for hepatitis C virus.	B182 and B171
Coronary artery procedures*	Replacement of the ascending thoracic aorta and horizontal aorta with aortic valve replacement, with reimplantation of the coronary arteries, by thoracotomy with extracorporeal circulation	CCAM procedure code: DGKA014
	Ascending thoracic aorta replacement without aortic valve replacement, with coronary artery reimplantation, by thoracotomy with extracorporeal circulation	CCAM procedure code: DGKA003

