	Replacement of the ascending thoracic aorta and horizontal aorta without aortic valve replacement, without reimplantation of the coronary arteries, by thoracotomy with extracorporeal circulation	CCAM procedure code: DGKA001
	Ascending thoracic aorta replacement with aortic valve replacement, with coronary artery reimplantation, by thoracotomy with extracorporeal circulation	CCAM procedure code: DGKA015
	Ascending thoracic aorta replacement with aortic valve replacement, without coronary artery reimplantation, by thoracotomy with extracorporeal circulation	CCAM procedure code: DGKA011
	Ascending thoracic aorta replacement without aortic valve replacement, without coronary artery reimplantation, by thoracotomy with extracorporeal circulation	CCAM procedure code: DGKA025
	Replacement of the ascending thoracic aorta and horizontal aorta without aortic valve replacement, with reimplantation of the coronary arteries, by thoracotomy with extracorporeal circulation	CCAM procedure code: DGKA026

Comorbidity	Definition	Codes (ICD-10 codes, ATC codes, CCAM procedure codes)
	Replacement of the ascending thoracic aorta and horizontal aorta with aortic valve replacement, without coronary artery reimplantation, by thoracotomy with extracorporeal circulation	CCAM procedure code: DGKA018
	Coronary revascularisation with 2 arterial and 3 venous grafts with 3 distal anastomoses, by thoracotomy with extracorporeal circulation	CCAM procedure code: DDMA005
	Coronary revascularisation using 3 arterial grafts with 3 distal anastomoses, by thoracotomy with extracorporeal circulation	CCAM procedure code: DDMA003
	Coronary revascularisation using 2 arterial grafts with 3 distal anastomoses, by thoracotomy with extracorporeal circulation	CCAM procedure code: DDMA006
	Coronary revascularisation using 2 arterial grafts with 4 or more distal anastomoses, by thoracotomy with extracorporeal circulation	CCAM procedure code: DDMA008
	Coronary revascularization with 3 arterial and 4 or more distal venous grafts by thoracotomy with extracorporeal circulation	CCAM procedure code: DDMA012
	Coronary revascularisation by arterial and venous graft with 2 distal anastomoses, by thoracotomy with extracorporeal circulation	CCAM procedure code: DDMA011

^{*} Revascularisation procedures are part of the definition of coronary artery disease. Final list of procedures will be fine-tuned based on medical advice and data distribution.

Pregnancy, ICD-10 codes

Pregnancy cessation	

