Spontaneous abortion	O03
Medical abortion	O04
Other abortion	O05
Unspecified abortion	O06
Preterm labour and delivery	O60
Single delivery by forceps and vacuum extractor	O81
Single delivery by caesarean section	O82

Pregnancy cessation	ICD-10
Other assisted single delivery	O83
Multiple delivery	O84
Ectopic pregnancy	O00
Hydatidiform mole	O01
Other abnormal products of conception	O02
Failed attempted abortion	O07
Complications following abortion and ectopic and molar pregnancy	O08
Pre-existing hypertension complicating pregnancy, childbirth and the puerperium	O10
Pre-existing hypertensive disorder with superimposed proteinuria	O11
Gestational [pregnancy-induced] oedema and proteinuria without hypertension	O12
Gestational [pregnancy-induced] hypertension without significant proteinuria	O13
Gestational [pregnancy-induced] hypertension with significant proteinuria	O14
Eclampsia	O15
Unspecified maternal hypertension	O16
Haemorrhage in early pregnancy	O20
Excessive vomiting in pregnancy	O21
Venous complications in pregnancy	O22
Infections of genitourinary tract in pregnancy	O23
Diabetes mellitus in pregnancy	O24
Malnutrition in pregnancy	O25
Maternal care for other conditions predominantly related to pregnancy	O26
Abnormal findings on antenatal screening of mother	O28
Complications of anaesthesia during pregnancy	O29

Malignant cancer (except skin cancer)

ICD-	Description
10	
C00	Malignant neoplasm of lip
C01	Malignant neoplasm of base of tongue
C02	Malignant neoplasm of other and unspecified parts
C03	Malignant neoplasm of gum
C04	Malignant neoplasm of floor of mouth
C05	Malignant neoplasm of palate
C06	Malignant neoplasm of other and unspecified parts
C07	Malignant neoplasm of parotid gland
C08	Malignant neoplasm of other and unspecified major salivary glands
C09	Malignant neoplasm of tonsil
C10	Malignant neoplasm of oropharynx
C11	Malignant neoplasm of nasopharynx
C12	Malignant neoplasm of pyriform sinus

ICD- 10	Description
C13	Malignant neoplasm of hypopharynx
C14	Malignant neoplasm of other and ill-defined sites in the lip, oral cavity and pharynx
C15	Malignant neoplasm of oesophagus
C16	Malignant neoplasm of stomach
C17	Malignant neoplasm of small intestine
C18	Malignant neoplasm of colon
C19	Malignant neoplasm of rectosigmoid junction
C20	Malignant neoplasm of rectum
C21	Malignant neoplasm of anus and anal canal
C22	Malignant neoplasm of liver and intrahepatic bile
C23	Malignant neoplasm of gallbladder

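### Several Annex 11 code lists do not match the Table 3 variables they serve

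*Protocol*

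**What the plan says.** The variables are defined in Protocol Section 9.3.1 (Table 3) and most of their codes are in Annex 11.

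- **VTE factor.** Table 3 lists inherited coagulation disorder among the VTE risk factors, once at baseline and once during treatment ("Defined as ≥1 ICD-10 diagnosis code for inherited coagulation disorder while receiving tofacitinib therapy"). It counts towards having at least one VTE risk factor and towards the VTE score, which is "Calculated as the sum of the number of VTE risk factors (as listed and defined above) identified in the 12 months prior" to the index dispensing. Section 9.7.2.4.1 also tabulates each VTE factor on its own. The Annex 11 codes are "D680, D681, D682, D66, D67, D689 and D686".
- **CV factor.** During treatment, coronary artery disease is "Defined as ≥1 ICD-10 diagnosis code for MI or stroke or ≥1 procedure code for CABG or PCI while receiving tofacitinib therapy". The baseline version has the same four components. Annex 11 gives I20-I25, I77 and Z95 for coronary heart disease, followed by a list of CCAM procedures with the footnote "Revascularisation procedures are part of the definition of coronary artery disease".
- **Comorbidity.** Diverticulitis is coded "Q396, Q696, K225, K382, N323, Q430, K314, N361 and C173".
- **Pregnancy.** Table 3 points to Annex 11 for the complete list of pregnancy codes. The single-delivery entries begin at "Single delivery by forceps and vacuum extractor" (O81).

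Section 9.3.1 describes the codes as preliminary, to be reviewed before study start and open to refinement in the SAP.

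**The concern.** A claims study measures what its code lists pick up. Under the printed coagulation list, a patient with haemophilia counts as having a thrombotic risk factor, while a patient coded only with inherited thrombophilia does not. The resulting row of the VTE table would describe mainly bleeding disorders under a label that suggests the opposite.

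Coronary artery disease feeds the CV proportion and CV score that Section 9.7.2.4.3 compares between reporting periods by regression, and the UC maintenance-dose outcome of Section 9.7.2.5.1. If half of the defined components have no code of their own, the variable analysed is not the variable defined.

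Pregnancy is a contraindicated-use outcome. Under-ascertainment there would make practice look better than it is. Diverticulitis matters less, because it appears only in the descriptive comorbidity tables.

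**Working it through.** The protocol states no figure to reproduce. The check sets each list beside the definition it serves and counts codes. Annex 11 prints no meanings for the individual D codes, and neither K57 nor O80 appears in it, so those readings use standard ICD-10 nomenclature. The stroke, PCI, aortic-procedure and C173 points can be seen from the protocol alone.

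**(a) Inherited coagulation disorder, 7 codes**
- Bleeding disorders: D66 and D67 (haemophilia A and B), D680 (von Willebrand disease), D681 and D682 (clotting-factor deficiencies) = 5.
- Unspecified: D689 = 1.
- Other thrombophilia: D686 = 1.
- Primary thrombophilia, D685: not listed.
- Total: 5 + 1 + 1 = 7.

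Reach into the aggregate measures: let p be the share of initiators carrying one of the bleeding codes, which the document does not give. Each such patient adds 1 to the score, so the mean score rises by at most p. The proportion with at least one factor rises only through patients with no other factor, so by at most p. If a share q has another factor independently, the rise is p × (1 − q). Section 9.5 puts the share with one or more risk factors of interest at 30% to 80%. Using that as q gives 0.7p at q = 0.30 and 0.2p at q = 0.80. The smallest difference in Table 5 is 10 percentage points. Reaching it would need p of at least 10% on the bound, or 10/0.7 = 14.3% to 10/0.2 = 50% under independence. Missed thrombophilia patients pull the other way.

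**(b) Coronary artery disease, 4 components in Table 3**
- MI: covered, since it lies within I20-I25.
- CABG: covered by DDMA003, 005, 006, 008, 011 and 012 = 6 procedures.
- Stroke: no code anywhere in Annex 11.
- PCI: no procedure code.
- The other procedures are ascending-aorta replacements: DGKA001, 003, 011, 014, 015, 018, 025 and 026 = 8. Of these, 001, 011, 018 and 025 are described as without coronary reimplantation = 4.
- Total: 6 + 8 + 0 PCI = 14.

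Two of four components (stroke and PCI) therefore have no code of their own. A patient whose only qualifying event is stroke meets Table 3 but is not found. A PCI patient is found only through another listed code, such as one in I20-I25 or Z95.

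**(c) Diverticulitis, 9 codes**
- From K57 (diverticular disease of intestine): 0.
- C173: 1. The malignancy table in the same annex labels C17 as a cancer of the small intestine, so one code serves both variables.

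**(d) Pregnancy, delivery categories O80 to O84**
- Listed: O81 (forceps or vacuum), O82 (caesarean), O83 (other assisted), O84 (multiple) = 4 of 5. O60 (preterm) is listed separately.
- Not listed: O80, single spontaneous delivery.

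**The case against.** The strongest reply is that the lists are not final. Section 9.3.1 says so, the footnote to the coronary procedures says that list will be adjusted on medical advice, and final code lists commonly belong in the SAP, which is not shown. This stands as to timing: it is a correction to make at finalisation. It does not make the printed codes right. Exchanging bleeding disorders for thrombophilia, or adding a whole component of a definition, changes what is measured and goes beyond refinement.

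Several stronger readings are tempting and are not supported:

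- A reader might infer that the coronary list omits its main event, or that PCI patients count as free of coronary disease. It does not omit it: MI lies within I20-I25 and bypass is coded. Many PCI patients would carry an I20-I25 code, and by standard meaning Z95 includes coronary implants.
- A reader might infer that pregnancies ending in spontaneous delivery are lost and that contraindicated use will be falsely low. Table 3 relies on SNDS-specific algorithms, Section 9.7.2.3.1 cites published ones, and Annex 11 also lists codes for conditions during pregnancy. The missing code is a risk whose realisation depends on the algorithm.
- A reader might infer that the between-period comparisons are biased. The same lists apply in every period, inherited coagulation disorder is one of ten VTE factors beside age, hypertension and diabetes, and counts of codes are not counts of patients.
- Diverticulitis might be taken for an adherence outcome. Table 3 gives it the role of comorbidity only.

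**Conclusion.** Annex 11 and Table 3 do not agree for four variables, and the printed lists should not be used as they stand.

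- The coagulation list is the clearest fault: 5 of 7 codes point away from thrombotic risk and primary thrombophilia is missing. The individual-factor row would be wrong however rare the codes are. The effect on having at least one VTE risk factor and on the score is probably small, on the assumption that inherited disorders are rare among initiators.
- For coronary artery disease, stroke-only patients are missed and some PCI patients may be. Eight aortic procedures are also counted, four of them without coronary reimplantation.
- The diverticulitis list includes a malignancy code and lacks the intestinal disease, which affects descriptive tables only.
- The pregnancy list carries a risk of under-ascertainment that cannot be settled without the algorithm.

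No size of bias can be computed, because the protocol gives no code frequencies. Parts (a) and (d) and the K57 part of (c) rest on standard ICD-10 meanings. The rest can be read from the protocol itself.

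**What to change.** Reconcile Annex 11 with Table 3 before the code lists are locked:

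- **Inherited coagulation disorder:** use D685, keep D686 only if other thrombophilia is intended, and drop D66, D67, D680, D681, D682 and D689.
- **Coronary artery disease:** add ICD-10 codes for stroke and CCAM codes for PCI, and remove the eight aortic-replacement procedures.
- **Diverticulitis:** use K57 and remove C173.
- **Pregnancy:** add O80 and check the list against the SNDS pregnancy algorithm actually adopted.

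The cost is an edit to the code lists before extraction. It needs no new data, no extra patients and no change to the analysis methods.
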